3.2.5.4.9 Second Course Phase

Patients may be eligible to receive pembrolizumab (MK-3475) in the Second Course Phase of this study if the study remains open and the patient meets the following conditions:

- Stopped initial treatment with pembrolizumab (MK-3475) after attaining an investigator-determined confirmed CR according to irRC
- Stopped initial treatment with pembrolizumab (MK-3475) after attaining investigator-determined confirmed SD, or PR, after 2 years of treatment with pembrolizumab (MK-3475)
- Was treated for at least 24 weeks with pembrolizumab (MK-3475) before discontinuing therapy
- Experienced an investigator-determined progression after stopping their initial treatment with pembrolizumab (MK-3475)

- Did not receive any other systemic anti-cancer treatment since the last dose of pembrolizumab (MK-3475); (local treatment such as radiation or surgery as anti-cancer therapy is allowed; Sponsor consultation must be obtained and subjects should have recovered completely from side effects of local procedures. In patients with brain metastases, neurological stability must be documented before initiating pembrolizumab.)
- Have a performance status of 0 or 1 on the ECOG Performance Scale
- Demonstrate adequate organ function as detailed in Section 2.2
- Female patient of childbearing potential should have a negative urine or serum pregnancy test within 72 hours prior to receiving retreatment with study medication.
- Female subjects of childbearing potential must be willing to use an adequate method of contraception as outlined in Section 3.2.4.2 – Contraception, for the course of the study through 120 days after the last dose of study medication.
- Note: Abstinence is acceptable if this is the usual lifestyle and preferred contraception for the subject.
- Male subjects of childbearing potential must agree to use an adequate method of contraception as outlined in Section 3.2.4.2 - Contraception, starting with the first dose of study therapy through 120 days after the last dose of study therapy.
- Note: Abstinence is acceptable if this is the usual lifestyle and preferred contraception for the subject. Does not have a history or current evidence of any condition, therapy, or laboratory abnormality that might interfere with the patient's participation for the full duration of the trial or is not in the best interest of the patient to participate, in the opinion of the treating investigator.
- Patients are encouraged to obtain a biopsy before receiving pembrolizumab (MK-3475) in second course phase.

Patients who restart treatment will be retreated at the 200 mg every 3 week dose and schedule of pembrolizumab (MK-3475).

3.2.5.5 Survival Status

To ensure current and complete survival data is available at the time of database locks, updated survival status and its respective entry into the database may be requested during the course of the study by the Sponsor. For example, updated survival status may be requested prior to but not limited to an external Data Monitoring Committee (eDMC) review, interim and/or final analysis. Upon Sponsor notification, all participants who do not/will not have a scheduled study visit or study contact during the sponsor defined time period will be contacted for their survival status (excluding participants that have previously recorded a death event in the collection tool).

3.2.5.6 Interim Data Locks

Part A

An interim data clean and lock will occur when Part A patient accrual is complete and all patients have completed Cycle 1. The purpose of this interim lock is preliminary analysis of safety, PK and PD, and determination of MTD and preliminary RP2D.

Part B

In addition to the two planned interim analyses (see Section 3.5.8), an interim data clean and lock will occur when Part B patient accrual is complete and all patients have (1) discontinued the study, or (2) been lost to follow up, or (3) been on study treatment for at least 6 months from the start of study therapy, whichever occurs first. The purpose of this interim lock is analysis of safety and efficacy data for administrative program decisions and for external reporting, respectively.

At the time of interim locks in Part A and B, patients may continue study therapy as per protocol guidelines. Study procedures will continue to be followed as per protocol.

Additional interim analyses for Part C, D and F are described in Section 3.5.

3.2.5.7 Discontinuation/Withdrawal from Study

Subjects/patients may withdraw at any time or be dropped from the study at the discretion of the investigator should any untoward effects occur. A subject may discontinue from study treatment but should continue to be followed up for survival. In addition, a subject/patient may be withdrawn by the investigator or the SPONSOR if he/she violates the study plan or for administrative and/or other safety reasons. The investigator or study coordinator must notify the SPONSOR immediately when a subject/patient has been discontinued/ withdrawn due to an adverse experience (telephone or FAX). When a subject/patient discontinues/withdraws prior to study completion, all applicable activities scheduled for the final study visit should be performed at the time of discontinuation. Any adverse experiences which are present at the time of discontinuation/withdrawal should be followed in accordance with the safety requirements outlined in Section 3.4 SAFETY MEASUREMENTS - DETAILS.

Subjects/patients who discontinue from the study for reasons unrelated to the study (e.g., personal reasons) will be replaced as required for the study to meet its objectives. The decision to remove a subject/patient and to replace dropouts will be made jointly by the investigator, SPONSOR Clinical Monitor, and SPONSOR study statistician. The replacement will generally receive the same treatment or treatment sequence (as appropriate) as the allocation number replaced. Both the replacement and originally allocated number will be unique numbers.

Discontinuation of study treatment does not represent withdrawal from the study.

3.2.5.8 Withdrawal from Future Biomedical Research

Subjects may withdraw their consent for Future Biomedical Research and have their specimens and all derivatives destroyed. Subjects may withdraw consent at any time by writing to the principal investigator for the main trial. If medical records for the main trial are still available, the investigator will contact the Sponsor using the designated mailbox ([contact]), and a form will be provided by the Sponsor to obtain appropriate information to complete specimen withdrawal. Subsequently, the subject's specimens will be removed from the biorepository and be destroyed. A letter will be sent from the Sponsor to the investigator confirming the destruction. It is the responsibility of the investigator to inform the subject of completion of destruction. Any analyses in progress at the time of request for destruction or already performed prior to the request being received by the Sponsor will continue to be used as part of the overall research trial data and results. No new analyses would be generated after the request is received.

In the event that the medical records for the main trial are no longer available (e.g., if the investigator is no longer required by regulatory agencies to retain the main trial records) or the specimens have been completely anonymized, there will no longer be a link between the subject's personal information and their specimens. In this situation, the request for specimen destruction cannot be processed.

3.3 EFFICACY / PHARMACOKINETIC / IMMUNOGENICITY, ETC. MEASUREMENTS

3.3.1 Efficacy Measurements

All baseline efficacy evaluations should be performed as close as possible to the beginning of treatment. Baseline imaging must be performed no more than 30 days before enrollment. The same imaging method should be used to characterize each identified and reported lesion at baseline and during follow-up.

Tumor status will be compared to baseline and response will be evaluated by physical examination, anatomic imaging measurement, serum tumor markers (where appropriate), and performance status.

With Amendment 10, imaging will be investigator assessed only. Imaging will not be assessed by central imaging vendor. Subjects may obtain scans locally.

3.3.1.1 Response Criteria

For Parts A, B, C, D and F, tumor response will be determined by investigator assessment.

In Part A, RECIST 1.1 (Appendix 6.3) will be applied for assessment of tumor response. The specific criteria are described in the Investigator's Imaging Operations Manual (IIOM).

In Part B, the irRC (investigator assessment) will be applied as a measure for assessment of tumor response and as basis for all protocol guidelines related to disease status (e.g., discontinuation of study therapy). The irRC system is specifically described in the IOM and in Appendix 6.5. RECIST 1.1 will also be applied as a measure for assessment of tumor response.

In Part C, the irRC (investigator assessment) will also be applied as a measure for assessment of tumor response and as basis for all protocol guidelines related to disease status (e.g., discontinuation of study therapy). The irRC system is specifically described in the IOM and in Appendix 6.5. RECIST 1.1 will also be applied as a measure for assessment of tumor response.

In Part D, the irRC (investigator assessed) will be applied as a measure for assessment of tumor response and as basis for all protocol guidelines related to disease status (e.g., discontinuation of study therapy). The irRC system is specifically described in the IOM and in Appendix 6.5. RECIST 1.1 will also be applied as a measure for assessment of tumor response.

In Part F, the irRC (investigator assessment) will also be applied as a measure for assessment of tumor response and as basis for all protocol guidelines related to disease status (e.g., discontinuation of study therapy). The irRC system is specifically described in the IOM and in Appendix 6.5. RECIST 1.1 will also be applied as a measure for assessment of tumor response.

The irRC is a recently published set of guidelines proposed for immunotherapies in solid tumors [18]. The guidelines were prompted mostly by the clinical observation that some patients can have a temporary increase in existing tumor lesions or the transient occurrence of a new lesion after start of immunotherapy, while ultimately experiencing treatment benefit in form of an objective disease response or long lasting disease stabilization. Analysis of more than 200 patients with MEL who had received study therapy with ipilimumab showed approximately 10% of patients falling into that category. This subgroup of patients had an overall survival that was comparable to that in patients who had a CR, PR or SD on the basis of traditional WHO criteria [18].

3.3.1.2 Efficacy Endpoints

Part A

In Part A, overall response rate will be used to estimate anti-tumor activity. If applicable, response duration will be determined. Response duration will be measured from first documentation of response to first documentation of disease progression. No other efficacy endpoints will be analyzed in Part A.

Part B

RR and DCR will serve as primary efficacy endpoints for the ipilimumab-naïve population treated at 10 mg/kg in Part B enrolled through Amendment 4 for internal

decision making, and the study in this population is considered positive (i.e., demonstration of proof-of-concept in this population) if the outcome in either endpoint is positive. The primary endpoint is RR based on RECIST 1.1 by independent central review to further demonstrate the anti-tumor activity of pembrolizumab (MK-3475) in all populations and dose/schedules in Part B. DCR, response duration, PFS and OS will serve as secondary endpoints.

Part C

In Part C, the primary endpoint is RR based on RECIST 1.1 by independent central review. DCR, response duration, PFS and OS will serve as secondary endpoints.

Part D

In Part D, the primary endpoint is RR based on RECIST 1.1 by independent central review. DCR, response duration, PFS and OS will serve as secondary endpoints.

Part F

In Part F, the primary endpoint is RR based on RECIST 1.1 by independent central review. DCR, response duration, PFS and OS will serve as secondary endpoints.

3.3.1.3 Radiographic Assessment

In all patients (Parts A, B, C, D and F), baseline tumor imaging (CT or MRI, with a preference for CT) examinations must be performed within 30 days before enrollment. The same imaging technique as used at baseline has to be used throughout the study.

Parts A, B, and D:

Tumor imaging will be performed approximately every 16 weeks (112 days) (± 28 days) from the first dose of study medication through Year 3, and then Q6 months (24 weeks) (± 28 days) through Years 4 and 5. After 5 years, imaging will be performed annually or per institutional standard of care. Response status will be assessed by the study site. Refer to Section 3.3.1.3 of the protocol for additional information. The same imaging technique must be used in a patient throughout the study. After first documentation of response or progression, repeat imaging will be required approximately 4 weeks later for confirmation, as per immune related response criteria (irRC) guidelines (see Appendix 6.5) (see Section 2.4.1).

Parts C and F:

Tumor imaging will be performed approximately every 9 weeks (63 days) (± 28 days) from the first dose of study medication through Year 2, then Q16 weeks (112 days) (± 28 days) through Year 3, and Q6 months (24 weeks) (± 28 days) through Years 4 and 5. After 5 years, imaging will be performed annually or per institutional standard of care. Response status will be assessed by the study site. Refer to Section 3.3.1.3 of the protocol for additional information. If a tumor biopsy was obtained from a target lesion during

eligibility assessment, it is preferred to obtain a new baseline scan. The same imaging technique must be used in a patient throughout the study. After first documentation of response or progression, repeat imaging will be required approximately 4 weeks later for confirmation, as per immune related response criteria (irRC) guidelines (see Appendix 6.5) (see Section 2.4.1).

Parts A, B, D, C, and F

If imaging shows PD, it is at the discretion of the investigator to keep a patient on study treatment or to stop study treatment until repeat imaging will be repeated approximately 4 to 6 weeks later, in order to confirm PD. Patients that are deemed clinically unstable are not required to have repeat imaging for confirmation. This decision will be based on clinical judgment of a patient's overall clinical condition, including performance status, clinical symptoms, and laboratory data. Section 2.4.1 lists the criteria for determining clinical stability. If repeat imaging shows an objective response or stable disease, treatment with pembrolizumab (MK-3475) will continue/ resume per imaging schedule. If repeat imaging confirms PD, patients will be discontinued from study therapy or permitted to continue treatment if the investigator believes patient is deriving benefit with sponsor consultation. This clinical judgment decision by the site should be based on the subject's overall clinical condition, including the following parameters:

- 1) Absence of symptoms and signs indicating clinically significant progression of disease, including worsening of laboratory values
- 2) No decline in ECOG performance status
- 3) Absence of rapid progression of disease
- 4) Absence of progressive tumor at critical anatomical sites (e.g., cord compression) requiring urgent alternative medical intervention

The same paradigm for confirmatory scans of response (4 weeks after the initial finding) or progression of disease (4-6 weeks after the initial finding) is applicable to subsequent planned scanning intervals

3.3.2 Pharmacokinetic Measurements

Details on collection of blood samples, processing, storage, and shipping will be provided in the Procedures Manual.

PK samples will be collected every 4 cycles and 30 days after discontinuation of study drug (or until the subject starts new cancer therapy). All pre-dose trough samples should be drawn within 24 hours before infusion of pembrolizumab.

The accumulation of robust PK and ADA data has allowed for the adequate characterization the clinical pharmacology of pembrolizumab across indications. With Amendment 10 ADA samples were no longer collected. Upon approval of Amendment 11 each site will stop the collection of PK samples for all subjects. Blood samples for PK and ADA may be stored. Analysis will be performed only if required.

3.3.3 Biomarkers

The primary biomarker objective is to assess the relationship between PD-L1 expression levels and anti-tumor activity of MK 3475 in patients with MEL and NSCLC.

The study of single dose nivolumab published data from nine patients who had tissue biopsies from their tumors that were tested for expression of PD-L1 by immunohistochemistry. Three of four patients who demonstrated membranous staining for PD-L1 had regression of their tumor burden. The fourth patient that demonstrated membranous staining for PD-L1 had been treated at the lowest tested dose in the protocol (0.3 mg/kg) and did not experience regression of tumor burden. The remaining five patients who provided tumor tissue for testing did not express PD-L1 and did not experience any clinical response. The authors of this paper believed that a potentially significant correlation between membranous PD-L1 staining on tumor cells and the likelihood of tumor regression following treatment with nivolumab existed with a two-sided p-value of 0.0476 by Fischer's exact test [17].

Therefore, PD-L1 expression levels will be measured in MEL and NSCLC tumor tissues by immunohistochemistry (IHC) performed on tumor tissue on glass slides. Statistical details for the biomarker analyses are described in Section 3.5 (Statistical Analysis Plan).

Other candidate biomarkers which will be investigated in the study may include, but are not limited to, the following:

- PD-L2 expression levels and TILs in biopsy tissue
- RNA and DNA profiling (genomic research) in biopsy tissue and blood samples
- Quantitative RNA expression of candidate genes of interest (including PD-L1)
- Targeted and global proteomics in biopsy tissue
- Cytokine/chemokine profiles in peripheral blood
- Proteomics and RNA signature profiling in peripheral blood

3.4 SAFETY MEASUREMENTS

3.4.1 Clinical and Laboratory Measurements for Safety

Vital signs, weight, physical examinations, ECOG performance status, ECGs and laboratory safety tests (e.g., CBC, serum chemistries, thyroid function,) will be obtained and assessed at designated intervals throughout the study (see Study Flow Chart, Section 1.7). Special attention will be given to immune-related adverse events (e.g., gut, skin, liver, endocrine organs, others).

Adverse events will be graded and recorded throughout the study according to NCI-CTCAE, version 4.0. Characterization of toxicities will include severity, duration, and time to onset. Safety endpoints will include all types of adverse events, in addition to laboratory safety assessments, ECOG performance scale status, ECGs, and vital signs.

3.4.2 Recording Adverse Experiences

An adverse experience is defined as any unfavorable and unintended change in the structure, function, or chemistry of the body temporally associated with the use of the SPONSOR's product, whether or not considered related to the use of the product. Any worsening (i.e., any clinically significant adverse change in frequency and/or intensity) of a preexisting condition which is temporally associated with the use of the SPONSOR's product, is also an adverse experience.

Changes resulting from normal growth and development which do not vary significantly in frequency or severity from expected levels are not to be considered adverse experiences. Examples of this may include, but are not limited to, teething, typical crying in infants and children, and onset of menses or menopause occurring at a physiologically appropriate time.

Adverse events may occur during clinical trials, or as prescribed in clinical practice, from overdose (whether accidental or intentional), from abuse and from withdrawal.

Progression of the cancer under study is not considered an adverse event.

All adverse events that occur after the consent form is signed but before treatment allocation/randomization must be reported by the investigator if they cause the subject to be excluded from the trial, or are the result of a protocol-specified intervention, including but not limited to washout or discontinuation of usual therapy, diet, placebo treatment or a procedure.

From the time of treatment allocation/randomization through 30 days following cessation of treatment, all serious adverse events and drug related AEOSI must be reported by the investigator. Such events will be recorded at each examination on the Adverse Event case report forms/worksheets. The reporting timeframe for adverse events meeting any serious criteria is described in section 3.4.5.1. The investigator will make every attempt to follow all subjects with non-serious adverse events for outcome.

With Amendment 10, investigators are required to report drug related NSAEs if they meet criteria for AEOSI (refer to the *Pembrolizumab AEOSI Preferred Term List* document) or are ECIs described in Section 3.4.8 below. Previous ECI guidance is now updated in Amendment 10 and is no longer required to be reported to Merck safety group. Other NSAEs do not need to be reported.

Electronic reporting procedures can be found in the EDC data entry guidelines. Paper reporting procedures can be found in the Investigator Trial File Binder (or equivalent).

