	Possibly related	There is evidence of exposure to the test drug. The temporal sequence of the AE onset relative to administration of the test drug is reasonable. The AE could have been due to another equally likely cause. Dechallenge (if performed) is positive.
No, there is not a reasonable possibility of drug relationship		Subject did not receive the test drug OR temporal sequence of the AE onset relative to administration of the test drug is not reasonable OR there is another obvious cause of the AE. (Also entered for a subject with overdose without an associated AE.) Depending on data collection method employed, drug relationship may be further graded as follows:
	Probably not related	There is evidence of exposure to the test drug. There is another more likely cause of the AE. Dechallenge (if performed) is negative or ambiguous. Rechallenge (if performed) is negative or ambiguous.
	Definitely not related	The subject/patient did not receive the test drug. OR Temporal sequence of the AE onset relative to administration of the test drug is not reasonable. OR There is another obvious cause of the AE.

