3.4.8 Events of Clinical Interest

Selected non-serious and serious adverse events are also known as Events of Clinical Interest (ECI) and must be reported to the Sponsor.

For the time period beginning when the consent form is signed until treatment allocation/randomization, any ECI, or follow up to an ECI, that occurs to any subject must be reported within 24 hours to the Sponsor if it causes the subject to be excluded from the trial, or is the result of a protocol-specified intervention, including but not limited to washout or discontinuation of usual therapy, diet, placebo treatment or a procedure.

For the time period beginning at treatment allocation/randomization through 90 days following cessation of treatment, or 30 days following cessation of treatment if the subject initiates new anticancer therapy, whichever is earlier, any ECI, or follow up to an ECI, whether or not related to the Sponsor's product, must be reported within 24 hours to the Sponsor, either by electronic media or paper. Electronic reporting procedures can be found in the EDC data entry guidelines. Paper reporting procedures can be found in the Investigator Trial File Binder (or equivalent).

Events of clinical interest for this trial include:

1. An overdose of Sponsor's product, as defined in Section 3.4.3 and 3.4.3.1 - Definition of an Overdose for This Protocol and Reporting of Overdose to the Sponsor, that is not associated with clinical symptoms or abnormal laboratory results.
2. An elevated AST or ALT lab value that is greater than or equal to 3X the upper limit of normal and an elevated total bilirubin lab value that is greater than or equal to 2X the upper limit of normal and, at the same time, an alkaline phosphatase lab value that is less than 2X the upper limit of normal, as determined by way of protocol-specified laboratory testing or unscheduled laboratory testing.*

*Note: These criteria are based upon available regulatory guidance documents. The purpose of the criteria is to specify a threshold of abnormal hepatic tests that may require an additional evaluation for an underlying etiology. The trial site guidance for assessment and follow up of these criteria can be found in the Investigator Trial File Binder (or Administrative Binder, or equivalent).

All ECIs should be reported to the SPONSOR within 24 hours or, at least, on the following working day to the SPONSOR via facsimile (documentation is found in the Administrative Binder).

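### As worded, Section 3.4.2 confines reporting of non-serious ECIs to drug-related ones, contradicting Section 3.4.8; the practical exposure is a liver-test ECI that the site attributes to another cause

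*Combined protocol and SAP*

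**What the plan says.** Three statements in Section 3.4.2 (Recording Adverse Experiences) matter. With Amendment 10, "investigators are required to report drug related NSAEs if they meet criteria for AEOSI" (the sentence refers to a separate term list) "or are ECIs described in Section 3.4.8 below". Next: "Previous ECI guidance is now updated in Amendment 10 and is no longer required to be reported to Merck safety group". Last: "Other NSAEs do not need to be reported".

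Section 3.4.8 (Events of Clinical Interest) sets the ECI duty itself. From allocation, "through 90 days following cessation of treatment, or 30 days following cessation of treatment if the subject initiates new anticancer therapy", whichever is earlier, the report is owed for "any ECI, or follow up to an ECI, whether or not related to the" product, within 24 hours. Before allocation the duty is narrower: it covers ECIs that lead to exclusion or result from a protocol-specified intervention. The section closes by asking for all ECIs within 24 hours or at least by the next working day.

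It names two ECIs:

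- an overdose without symptoms or abnormal laboratory results;
- AST or ALT at or above 3 times ULN, with total bilirubin at or above 2 times ULN and alkaline phosphatase below 2 times ULN.

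The note to the second explains that the threshold flags liver tests whose cause may need further evaluation.

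**The concern.** Two current sections give a site different answers to the same question: does the investigator's causality call decide whether a non-serious ECI is reported? Under 3.4.2 as worded it does; under 3.4.8 it does not.

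The difference matters most for the liver-test ECI. A laboratory trigger with no causality condition sends the case to the Sponsor before the cause is settled. If the site's first attribution acts as a filter, the cases that most need a second look can be held back. An unrelated call is foreseeable in this trial. Section 2.2 admits patients with liver metastases at AST/ALT up to 5 times ULN, already above the 3-times component of the trigger (the bilirubin component must still be met). Table 3-4 in Section 3.4.6 assigns events with another obvious cause to the not-related category. At the same time, raised transaminases or bilirubin have their own row in the immune-related toxicity table (Table 3-2, Section 3.2.5.4.4), so the Sponsor has reason to want these cases promptly.

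**Working it through.** No sample size, power, error rate or event count is involved, so the check is a comparison of texts.

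**Step 1: what 3.4.2 requires.** The object of the verb is drug-related NSAEs. The two conditions that follow (meeting AEOSI criteria, or being an ECI) both describe that object. An ECI that is non-serious and judged unrelated is not a drug-related NSAE, so it drops into the residual sentence, "Other NSAEs do not need to be reported".

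**Step 2: whether the rest of 3.4.2 repairs this.** The preceding paragraph lists serious events and drug-related AEOSI through 30 days after treatment; it does not mention ECIs. The sentence on previous ECI guidance can be read as dropping ECI reporting generally or only the former list, so it adds doubt.

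**Step 3: 3.4.2 against the other sections, for each non-serious case.**

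| Event | 3.4.2 as worded | Other sections |
|---|---|---|
| Liver-test ECI, judged related | Reportable | 3.4.8: reportable within 24 hours |
| Liver-test ECI, judged unrelated | Not required | 3.4.8: reportable within 24 hours |
| Symptom-free overdose | Not within the drug-related category | 3.4.8, 3.4.3.1 and Table 3-4: reportable within 24 hours |

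A liver-test case that is also serious is outside the problem, because the serious-event rules in 3.4.5.1 apply irrespective of causality.

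**Step 4: the liver-test row.** For a non-serious, unrelated case, 3.4.8 is the only text that requires expedited reporting. Section 3.2.5.4.6 and the follow-up flow-chart footnotes call for AEs to be recorded or collected up to the Safety Follow-up Visit, but neither sets a 24-hour ECI report. Here 3.4.2 contradicts the only rule that protects prompt notice.

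**Step 5: the overdose row.** Table 3-4 places this case under the heading for no reasonable possibility of drug relationship: "Also entered for a subject with overdose without an associated AE". So it cannot meet the drug-related condition in 3.4.2. But 3.4.3.1 and Table 3-4 each require every overdose to be reported within 24 hours, with or without an adverse event, and 3.4.8 lists it again. The duty is stated three times outside 3.4.2.

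**The case against.** The best defence is that 3.4.2 sends the reader to 3.4.8, which is the specific ECI section, states its duty without regard to causality, and should govern. The ECI phrase in 3.4.2 can also be read as a separate category, in which case there is no conflict. Both readings are possible, and they may well be what was intended. They do not remove the problem, because the sentence is followed by a release of everything else, and a site should not have to choose the charitable reading to report correctly.

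Other parts of the defence stand in full and limit the point:

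- **Overdose.** A reader might infer that symptom-free overdoses go unreported. The documents do not support that, given the explicit duties in 3.4.3.1, Table 3-4 and 3.4.8. Moreover, under the definition in 3.4.2 an overdose with no unfavourable change is arguably not an adverse event at all, so the release of other NSAEs would not reach it.
- **Liver-injury count.** A reader might infer that the count is biased downward. That does not follow. All four analytes are in the protocol chemistry panel (Appendix 6.1). Laboratory assessments are a safety measure in their own right (Section 3.5.3.2) and are to be summarized (Section 3.5.5.5). The threshold can be counted from laboratory data whatever the causality call.
- **Number of cases.** A reader might want to apply an event rate to the 1260 enrolled patients. The documents give no rate for the trigger or for unrelated attributions. The disputed sentence applies only from Amendment 10, so the relevant patients are those then still in a reporting window; their number is not stated.
- **Scope.** Section 3.4.8 does not cover every ECI at any time. It has post-treatment limits and a separate pre-allocation condition.

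**Conclusion.** The contradiction is real and lies in current text. Section 3.4.2, read as worded, makes drug relationship a condition for reporting non-serious ECIs; Section 3.4.8 rules that condition out after allocation, within its windows. The consequence is confined to one situation: a non-serious liver-test ECI, judged unrelated, at a site that follows 3.4.2. What is at risk is expedited notification, not the laboratory data and not the overdose reports.

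The conclusion rests on the grammatical reading of 3.4.2 and on sites being able to act on that section alone. It needs no assumption about event rates, and no case estimate can be supported. This is a wording inconsistency with a safety-reporting consequence, and it should be corrected because the correction is nearly free.

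**What to change.** Reconcile 3.4.2 with 3.4.8 by splitting the sentence into two limbs, for example: *Investigators report (a) drug-related NSAEs that meet the AEOSI criteria; and (b) ECIs listed in Section 3.4.8, regardless of relationship to study drug, within the periods and under the conditions given in that section. NSAEs outside (a) and (b) are exempt.* Tying limb (b) to the periods and conditions of 3.4.8 keeps its pre-allocation rule and post-treatment windows intact.

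In the same edit, reword the sentence on previous ECI guidance so that it plainly refers to the former ECI list and not to the two ECIs that 3.4.8 now defines. Check that the data entry guidelines agree.

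The cost is two sentences in the protocol and a matching check of the guidelines. No assessment, analysis or new duty is added, since 3.4.8 already requires these reports.
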